Our Aim 2 will examine the long-term outcomes between patients who received BCS without SLNB and patients who received BCS with SLNB. Patients who received BCS in the beginning yet ended up with mastectomy for their primary DCIS will be excluded. For patients who received BCS plus RT, SLNB will not likely provide any benefits since RT is able to control small lesions. However, we plan to determine the effects of SLNB among patients who received BCS without RT, which will have important clinical implications.

The time period for defining the cohort for the Aim 1 will be between January 1998 and December 2011. Using medical claims for this cohort, we will identify any side effects within a

9-month window (from DCIS diagnosis to 9 months post-diagnosis). The time period for defining the cohort for the Aim 2 will be from January 1998 to December 2012, and patients will be followed from 9 months after DCIS diagnosis through the latest date to which data is available in SEER-Medicare. For instance, the next SEER-Medicare linked dataset will have overall mortality through December 2015, breast cancer specific mortality through December 2013, and claims data (to identify treated recurrence) through December 2014.

We identify interventions and comparators in our study using specific international classification of Diseases, Ninth Revision, (ICD-9) codes, CPT codes and HCPCS codes. We will limit our sample to DCIS patients who received BCS as their first surgery; that is, we exclude patients whose first surgery is mastectomy, because we are only interested in patients who receive less intensive treatment and their outcomes. Because SLNB is performed by a surgeon, we identify it within a window consistent with those used in prior literature to identify breast cancer surgery, that is, between the date of the first BCS and 6 months after DCIS diagnosis. We are aware that patients may receive BCS first and mastectomy later for their primary DCIS. Furthermore, we realize that SLNB may affect whether or not patients receive mastectomy.

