Based on the input of our patient and professional advisory committee members, we propose the following outcomes of interest in this project. In Aim 1 we focus on acute/sub-acute side effects. Secondary outcomes include treatment received. In Aim 2, our primary outcomes include breast cancer specific mortality, incident ipsilateral invasive breast cancer occurrence (based on ipsilateral invasive breast cancer from SEER) and treated recurrence (based on follow-up mastectomy). Secondary outcomes include overall survival and lasting side effects. Overall survival, expected to be similar, would be used as a benchmark outcome to check performance of our model.

In addition to the key exposures (interventions and comparators) and endpoints (outcomes of interest), we will further select covariates, including patient demographics, comorbidities, tumor characteristics and prior healthcare utilization, based on prior literature and our experience. We plan to include the following covariates to control for confounding. For patient demographics, we will include patient's age, sex, ethnicity, marital status and years of diagnosis. For geographical and social-economical characteristics, we will include income, education and metropolitan residence. For patient's comorbidities, we plan to include Elixhauser comorbidity index, disability index and prior hospitalization. For DCIS characters, we will include grade, size, comedonecrosis and hormone receptor status. For health care system utilization, we will consider prior influenza vaccination, physician visit, MRI use and surgeon's volume. Last, to control for other treatment patients have received, we will adjust for mastectomy and radiation therapy.

Data management and statistical analysis

We plan to create a dataset for this project. Each patient in the SEER-Medicare dataset has a unique patient identification number. Using this information, we will be able to collect patient demographics and DCIS characteristics from the SEER registry as well as claims data from Medicare on what treatment patients have received or what side effects they have experienced. We will manage the dataset in a suitable manner that fully complies with the SEER-Medicare data use rules and confidentiality.

As a secondary data analysis, we will be unable to prevent missing data from the original dataset. We do, however, set a priori exclusion and inclusion criteria for the creation of our cohort. We

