will include only DCIS patients who have available claims data (i.e. are enrolled in fee-for-service coverage) during the period between cancer diagnosis and the end of the follow-up (Aim 1: 9 months after DCIS diagnosis; Aim 2: either death or the last date of claims released by SEER-Medicare). Statistically, we plan to create an “unknown” category to capture those patients who had a missing value. Additionally, we will conduct sensitivity analyses regarding whether or not excluding these patients would change our findings.

To compare baseline characteristics between intervention and control groups, we will conduct standard descriptive statistics using χ^2 tests for categorical variables and t-tests for continuous variables. We will tabulate the frequencies of outcomes of interests by the intervention vs. control group. We will use multivariable analyses to test our hypotheses while controlling for unbalanced covariates, as described below.

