We plan to control for selection bias using propensity score matching methodology.¹⁷ Specifically, the propensity score matching will be based on the Mahalanobis distance¹⁸ calculated using age, race, residence in a metropolitan county, comorbidity, prior influenza vaccination or prior visit to a primary care physician (both as proxies for access to care), income, preoperative MRI use, and tumor characteristics. Tumor characteristics include size, grade, comedonecrosis, and estrogen receptor status. By incorporating these factors in matching, we expect to substantially decrease bias and balance the risk for outcomes of interest between the SLNB and non-SLNB groups. We will use 2: 1 matching, as prior literature indicated that this approach results in improved precision without a commensurate increase in bias.¹⁹ To ensure robust and comprehensive matching, matches will be assigned by choosing the two best non-SLNB patient matches for each SLNB patient; when two or more SLNB patients match the same control (that is, have Mahalanobis distances minimized by the same control), one will be randomly selected as a match, and this process reiterates until all SLNB patients have two matched controls. We will assess the validity of the matching by comparing risk factors between the SLNB and non-SLNB groups using χ^2 tests. The difference in outcomes between the control and intervention groups will be estimated in a Kaplan-Meier curve. We will estimate the relative risk in the propensity score matched sample using the standard method for matched-pair data.²⁰ We will use the Cox proportional hazards models to investigate the association between various factors (grade, tumor size, and estrogen receptor status) and outcomes.²¹

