For multivariable analyses, we will use conditional logistic regression models for acute/subacute side effects (primary outcomes) and treatment received (mastectomy or radiation therapy; secondary outcomes) in Aim 1, with conditioning on the matched variable. For primary outcomes, we will run 2 models, with or without controlling for treatment received. We will report adjusted odds ratios of SLNB on these outcomes. In Aim 2, we will apply time-to-event models to test whether the intervention is associated with better outcomes, including primary and secondary outcomes. We will report adjusted hazard ratios of SLNB on these outcomes. The proportional hazards assumption will be evaluated for each model using a variety of methods (evaluation of Kaplan-Meier and log(-log) survival plots, Schoenfield residuals, and covariate x time interactions). If the proportional hazards assumption is violated, we will instead use parametric survival models, using AIC and BIC to determine the best parameterization (exponential, Weibull, generalized gamma, Gompertz, lognormal, or loglog). All time-to-event models will incorporate a shared frailty term for the matching group, and will include covariates that are not balanced by matching. These models will allow us to test for association between various factors (grade, tumor size, and estrogen receptor status) and outcomes.

In order to identify suitable patient subgroups that may be able to forego SLNB, we plan to explore the following stratification schemes in Aim 2 analysis: 1. Stratify patients by receipt of radiation therapy; 2. Stratify patients by key DCIS characteristics, including grade, comedonecrosis and tumor size; 3. Stratify patients by their predicted life expectancy, given their age, sex and comorbidities.

Expected outcomes of the study

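### Kaplan-Meier is named for the difference in all outcomes; if other-cause deaths are censored, it overstates the absolute risk of each Aim 2 primary outcome

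*Combined protocol and SAP*

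**What the plan says.** The matched comparison, under Data management and statistical analysis, reads: "The difference in outcomes between the control and intervention groups will be estimated in a Kaplan-Meier curve". The sentence is not limited to overall survival.

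Methodology lists the Aim 2 outcomes: "our primary outcomes include breast cancer specific mortality, incident ipsilateral invasive breast cancer occurrence", together with treated recurrence identified by follow-up mastectomy. Overall survival and lasting side effects are secondary. Overall survival is expected to be similar in the two groups and serves as a benchmark for the model.

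The required claims period ends, for Aim 2, at death or the end of data: "Aim 2: either death or the last date of claims released by SEER-Medicare". Expected outcomes of the study ends the survival timeframe the same way.

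The regression part of the plan is separate. Aim 2 uses Cox models, or parametric models if proportional hazards fails, and the reported measure is a ratio: "We will report adjusted hazard ratios of SLNB on these outcomes". The plan also explores strata, one of which is: "Stratify patients by their predicted life expectancy, given their age, sex and comorbidities".

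The text available for review does not mention competing risks, cumulative incidence or cause-specific hazards, and does not say how other-cause deaths enter the curves.

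**The concern.** Kaplan-Meier suits overall survival, where every death is an event. For the Aim 2 primary outcomes, a woman who dies of another cause can no longer have the event. Censoring her treats her as still at risk beyond the censoring time. One minus Kaplan-Meier then estimates the risk in a hypothetical setting without other-cause death, and this exceeds the proportion of women who actually have the event. The direction holds for any positive other-cause hazard; only the size depends on the rates.

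What is at stake is any absolute risk, or difference in absolute risk, read from these curves. The plan wants to identify women who could forgo sentinel lymph node biopsy (SLNB), and absolute risk bears on that. If curves are also drawn by predicted life expectancy, Kaplan-Meier would not show any lower absolute risk that is due to competing death.

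**Working it through.** The plan states no event rate, mortality rate, sample size or power, so there is no figure of its own to reproduce. All rates below are assumptions.

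**Formulas.** With constant endpoint hazard *l*, other-cause death hazard *d* and time *t* from the 9-month start:

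- one minus Kaplan-Meier, other-cause deaths censored: 1 − exp(−*l t*)
- cumulative incidence: *l*/(*l*+*d*) × [1 − exp(−(*l*+*d*) *t*)]

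**Risk in one group**, *l* = 0.006, *d* = 0.05 (range 0.03 to 0.07):

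- 5 years: 1 − exp(−0.03) = 2.96%. Cumulative incidence is 0.006/0.056 × [1 − exp(−0.28)] = 2.62%. The ratio is 1.13, so the risk is 13% too high. At *d* = 0.03 and 0.07, cumulative incidence is 2.75% and 2.50% (8% and 18% too high).
- 10 years: 1 − exp(−0.06) = 5.82%. Cumulative incidence is 0.006/0.056 × [1 − exp(−0.56)] = 4.59%, so the risk is 27% too high. At *d* = 0.03 and 0.07, cumulative incidence is 5.04% and 4.20% (16% and 39% too high).

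**Group difference**, no SLNB minus SLNB, hazard ratio 0.8 (*l* = 0.0048 with SLNB), *d* = 0.05 in both groups:

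| Horizon | Kaplan-Meier | Cumulative incidence |
|---|---|---|
| 5 years | 0.58 points | 0.52 points |
| 10 years | 1.14 points | 0.90 points |

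With a hazard ratio of 1 and equal *d*, both differences are 0.

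**Dependence on the endpoint rate**, 10 years, *d* = 0.05:

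| Endpoint hazard per year | Risk: Kaplan-Meier vs cumulative incidence | Difference at hazard ratio 0.8 |
|---|---|---|
| 0.1% | 1.00% vs 0.78% | 0.20 vs 0.16 points |
| 1.2% | 11.31% vs 8.94% | 2.15 vs 1.71 points |

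**Robustness.** With other-cause mortality rising 9% per year from a start of 1.5% to 3%, and endpoint hazards of 0.2% to 1.0% per year, the relative overstatement at 10 years is 10% to 22%.

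**Strata.** Suppose two life-expectancy strata share *l* = 0.006 and have *d* = 0.02 and 0.10. Ten-year Kaplan-Meier gives 5.82% in both; cumulative incidence gives 5.28% and 3.70%.

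**Follow-up.** Methodology sets the accrual window: "The time period for defining the cohort for the Aim 2 will be from January 1998 to December 2012". It gives the data end dates as "breast cancer specific mortality through December 2013, and claims data (to identify treated recurrence) through December 2014". To be followed for 10 years from month 9, a woman must be diagnosed by March 2003 for breast cancer mortality, or by March 2004 for treated recurrence. That is 63 or 75 months from January 1998. With even accrual over 180 months the shares are 35% and 42%. Study design gives 1998-2013 for Aim 2, which is 192 months, and the shares become 33% and 39%. For 5 years the counts are 123 and 135 months: 68% and 75% on the first window, 64% and 70% on the second.

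**The case against.** The strongest reply is that no listed main estimate is affected. Aim 2 hypotheses are tested with time-to-event models and reported as hazard ratios. Expected outcomes of the study lists ratio measures for the main analysis and measures of association for the strata, and promises no absolute risk at any horizon. That stands, and it limits the point to the curves and what is read from them. It does not remove the commitment to Kaplan-Meier as the estimator of the difference in outcomes.

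It is also fair that the effect on the group difference is modest when other-cause death is equal: about 0.07 points at 5 years in the example, and 0.04 points at 10 years for an endpoint of 0.1% per year.

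A reader might infer more, in three ways that the documents do not support:

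- *That the hazard ratios are biased by this.* They are not. If other-cause deaths are censored in the models, the estimates are cause-specific hazard ratios. The plan should say so, because it does not state how those deaths are handled.
- *That the benefit of SLNB could be badly misstated.* With other-cause death of 5% per year in controls and 3% with SLNB, the 10-year difference would be 1.14 points by Kaplan-Meier against 0.54 by cumulative incidence. This implies about 39% against 26% dead of other causes at 10 years (1 − exp(−0.5) and 1 − exp(−0.3)). The plan expects similar overall survival, checks it as a benchmark, and matches on age and comorbidity.
- *That the life-expectancy strata differ mainly in competing death, so that Kaplan-Meier will mislead there.* Nothing says endpoint hazards or hazard ratios are equal across strata, and curves by stratum are not promised. The strata example above only shows what Kaplan-Meier would hide under those conditions.

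**Conclusion.** The point holds in a limited form and should be fixed. The estimator named for the difference in outcomes is unsuitable for the three Aim 2 primary outcomes, and for lasting side effects, if other-cause deaths are censored. Censoring is the natural reading of follow-up that ends at death, but it is an inference.

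On that reading the upward bias in each group's absolute risk is certain in direction. Its size rests on assumed rates: roughly a tenth to a fifth at 5 years and a sixth to two fifths at 10 years in the main example. The group difference is exaggerated when there is a true effect and other-cause death is equal, and is undistorted when there is no effect. Overall survival, Aim 1 and the adjusted hazard ratios are not affected.

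**What to change.** Replace the Kaplan-Meier sentence with:

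> Overall survival will be shown by Kaplan-Meier. For breast cancer specific mortality, ipsilateral invasive cancer, treated recurrence and lasting side effects, cumulative incidence from 9 months after diagnosis will be estimated by matched group with the Aalen-Johansen method, with other-cause death as the competing event for breast cancer mortality and death from any cause for the others. Differences at 5 years, and at 10 years where follow-up allows, will be reported with 95% intervals that respect the matched sets.

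Use the same estimator for any curves drawn by stratum. State that other-cause deaths are censored in the Aim 2 Cox or parametric models for these endpoints, and label those estimates cause-specific. The Kaplan-Meier and log(-log) plots used to check proportional hazards can stay.

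The cost is a short wording change and a little more analysis, with standard software and data already held; the models do not change. Reported absolute risks will be slightly lower. The 10-year estimates will rest on about a third to two fifths of the cohort (33% to 42%, depending on the accrual window and endpoint, assuming even accrual).

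### If proportional hazards fails, the Aim 2 fallback offers no model in which the SLNB hazard ratio can cross 1, and three of its six models keep the constant ratio just rejected

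*Combined protocol and SAP*

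**What the plan says.** The rule is in the combined protocol and SAP, section Data management and statistical analysis, in the paragraph on multivariable models. For all Aim 2 outcomes, primary and secondary, it promises: "We will report adjusted hazard ratios of SLNB on these outcomes". Proportionality is to be checked for each model by "evaluation of Kaplan-Meier and log(-log) survival plots, Schoenfield residuals, and covariate x time interactions". The remedy is: "If the proportional hazards assumption is violated, we will instead use parametric survival models, using AIC and BIC to determine the best parameterization". The candidates are "exponential, Weibull, generalized gamma, Gompertz, lognormal, or loglog"; I read the last as log-logistic. The paragraph adds: "All time-to-event models will incorporate a shared frailty term for the matching group, and will include covariates that are not balanced by matching".

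The choice is not restricted to non-proportional families. SLNB is not said to act on a shape parameter, and no SLNB-by-time term or period-specific estimate is carried into the fallback. Interactions with time appear only as a diagnostic.

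Two other statements bear on this. The same section says: "The difference in outcomes between the control and intervention groups will be estimated in a Kaplan-Meier curve". The Methodology section says: "Overall survival, expected to be similar, would be used as a benchmark outcome to check performance of our model".

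**The concern.** A fallback for non-proportional hazards should be able to describe an effect that changes over time. This one may return the same constant ratio from a different likelihood. Where it does not, it forces the effect to keep one direction for the whole of follow-up. AIC and BIC do not guard against this, because they reward overall fit, and that is largely the shape of the baseline hazard.

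The rule covers every Aim 2 outcome over follow-up of up to about 15 to 17 years. Aim 2 is also meant to identify subgroups who could do without SLNB. If early and late effects differ in direction, one averaged ratio can mislead for both periods. The overall-survival benchmark is exposed too: a ratio near 1 is the expected result, so opposite early and late effects that average out would look like a pass.

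**Working it through.** **Inputs from the documents.** Six families, the AIC/BIC rule, matched-set frailty and 2:1 matching (Data management and statistical analysis). Aim 2 diagnoses start in January 1998 and follow-up starts at month 9, so in October 1998. Data run to "overall mortality through December 2015, breast cancer specific mortality through December 2013, and claims data (to identify treated recurrence) through December 2014" (Methodology). Maximum follow-up is therefore about 15.25 years for breast cancer mortality, 16.25 for claims and 17.25 for overall mortality. The plan gives no sample size, event rate or effect size, so there is no planned figure to reproduce.

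**1. Constant-ratio families.** With SLNB indicator x and coefficient b, the hazards are λ·exp(bx) (exponential), λp·t^(p−1)·exp(bx) (Weibull) and λ·exp(γt)·exp(bx) (Gompertz). In each, HR(t) = exp(b) at all t. That is 3 of 6.

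**2. Time-ratio families.** Let TR be the time ratio and r the hazard of log time. Then

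HR(t) = r(log t − log TR) / r(log t).

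The log-time densities of the lognormal, log-logistic and generalized gamma are log-concave, so r never decreases. If TR > 1, HR(t) ≤ 1 at every t; if TR < 1, HR(t) ≥ 1. The log-logistic has a closed form: with φ = 1/TR, scale λ and shape p,

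HR(t) − 1 = (φ^p − 1) / (1 + (φλt)^p),

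which has one sign for all t and shrinks to 0. A numerical grid with φ = 1.2, 2 and 4 agreed: the minimum HR was 1.03 (lognormal), 1.0000003 (log-logistic) and 1.000 to rounding (generalized gamma). For lognormal and log-logistic, log r is also concave, so HR(t) can only move toward 1. A delayed effect must then appear as an early effect that fades.

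**3. Survival curves and frailty.** Within a matched set, S1(t) is S0(t)^exp(b) or S0(t/TR), so the curves cannot cross. Averaging over a shared frailty keeps that order. Frailty adds no SLNB-by-time effect.

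**4. What AIC and BIC select (assumed inputs).**
- 1,000 sets of 1 SLNB patient and 2 controls; gamma frailty variance 0.5; control cumulative hazard 0.1 at year 10.
- Five baseline shapes and three SLNB patterns changing at year 4: 0.5 then 1.6, 1.0 then 0.6, 0.6 then 1.1.
- Uniform censoring from 1.25 to 16.25 years; mean events 212 to 285.
- 15 cells × 100 = 1,500 data sets. Proportionality was rejected at 5% in 664, and all six families were then fitted with shared gamma frailty.

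| Baseline hazard | Rejected | AIC chose constant-ratio family | BIC chose constant-ratio family |
|---|---|---|---|
| Rising | 126 | 119 (94%) | 126 (100%) |
| Constant | 150 | 128 (85%) | 141 (94%) |
| Falling | 171 | 123 (72%) | 126 (74%) |
| Early hump | 130 | 35 (27%) | 42 (32%) |
| Lognormal | 87 | 0 | 0 |

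Comparing HR at years 2 and 10, it crossed 1 in 0 of 664 × 6 = 3,984 fits.

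**5. What the selected model reports (geometric means).**
- Constant baseline, true 0.5 then 1.6: 1.09 at all times.
- Lognormal baseline, true 0.5 then 1.6: 1.39 at year 2 and 1.26 at year 8.
- Lognormal baseline, true 1.0 then 0.6: 0.67 at year 2 and 0.76 at year 8, so the order is reversed.
- One data set of 60,000 women for each of these two lognormal cases: 1.56 and 1.36, and 0.68 and 0.78. Sample size is not the cure.

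**6. A separate scenario.** True HR 2.0 before year 5 and 0.5 after, about 340 events, no frailty fitted. Proportionality was rejected in 112 of 113 data sets; among those, AIC chose a constant-ratio family in 18 (16%) and BIC in 22 (20%). Separate effects per period returned 1.99 and 0.47. A single Cox coefficient gave 1.26, the wrong side of 1 for the later period.

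**7. Cut-point sensitivity of the alternative.** In the 60,000-women lognormal data set with true 0.5 then 1.6, Cox interval ratios (without frailty) were 0.61 and 1.58 with a cut at year 3, and 0.91 and 1.71 with a cut at year 5. A cut at year 3 targets 0.5 for the early period, so 0.61 includes sampling error. A cut at year 5 mixes periods: control cumulative hazard is 0.0193 at year 4 and 0.0300 at year 5, giving roughly (0.5 × 0.0193 + 1.6 × 0.0107)/0.0300 = 0.89.

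**The case against.** The strongest reply is that the plan does not leave the reader with one number. The Kaplan-Meier sentence follows the matching step, so the curves are most naturally read as curves in matched women, and they can cross. A matched-pair relative risk is also planned. The fallback starts only after the diagnostics have shown the problem, so an SLNB-by-time estimate may already exist. The section Expected outcomes of the study names odds, rate or hazard ratios only as examples, so the effect measure is arguably open. This stands in part: the evidence of a changing effect might be seen. But the plan does not commit to reporting it, the curves are not adjusted for covariates left unbalanced, and the regression estimate it does promise cannot express a crossing.

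Second, the structural result needs SLNB to enter through one coefficient; letting it act on a shape parameter would allow a crossing. That is correct, but the plan does not say this will be done. The result also concerns the within-set ratio. With gamma frailty, the population-averaged ratio of a time-ratio family can pass 1. In the examples run, this came only once control survival had fallen to about 0.6 or lower (frailty variance up to 2) or to 0.75–0.86 (variance 4 to 8).

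Third, the simulated patterns are ones these families describe badly. For a waning effect on one side of 1 they do better: with 60,000 women, no frailty, a lognormal baseline and true 0.4 then 0.8, the selected lognormal gave 0.62 at year 2 and 0.75 at year 8, right in direction and order. With a constant baseline the figures were only 0.62 and 0.64. Generalized gamma can also let the ratio move away from 1. So the fallback is of partial use.

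Finally, the documents show no time-varying SLNB effect. That is true, but the plan itself provides for the contingency, and a contingency should work when it is triggered.

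**Conclusion.** The concern holds. Read as written, the rule can replace a rejected constant hazard ratio with another constant hazard ratio, and no candidate can show an SLNB effect that changes direction. This part is algebra and needs no event rates. It rests on three conditions: SLNB enters as an ordinary covariate, the ratio meant is the within-set one, and the sixth family is log-logistic (the count of three constant-ratio families depends on that). The three time-ratio families also do not, in general, yield one hazard ratio per outcome, so the promised measure is undefined if one of them is selected.

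The selection figures (0% to 94% by AIC, 0% to 100% by BIC) depend on assumed baselines, event rates and effect patterns. They show that the failure is possible and give no estimate of its frequency. The rule should be changed before outcomes are examined. It has no effect on the analysis if proportionality is not rejected.

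**What to change.** Replace the fallback as follows.

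- If SLNB violates proportionality, keep the Cox model with matched-set frailty and add an SLNB-by-time term, with its cut-points or functional form fixed and justified before outcomes are examined.
- Report interval-specific hazard ratios, or hazard ratios at named times, together with an absolute-risk or restricted mean survival difference at fixed times.
- If only an adjustment covariate violates proportionality, stratify on it or give it its own time interaction.
- Keep the parametric families, if at all, as a sensitivity analysis, and state the measure reported: a time ratio, or HR(t) at named times.
- Apply the same rule to the overall-survival benchmark, so that it is not judged on one averaged ratio.

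The cost is SAP wording and standard software; no new data are needed. There are drawbacks: several numbers with wider intervals instead of one, sensitivity to the cut-point (0.91 instead of 0.61 in the example), and later-interval ratios that compare only women still event-free. The documents offer no basis for a cut-point, so one must be argued for. The Cox interval figures above were fitted without frailty, so the exact model proposed here was not itself simulated.

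### The Aim 2 rule for leaving the Cox model is not tied to the SLNB term, so another covariate's non-proportionality can change how the SLNB effect is modelled and reported

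*Combined protocol and SAP*

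**What the plan says.** The rule is in the Combined protocol and SAP, section Data management and statistical analysis, in the paragraph on multivariable analyses.

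- **Promised measure.** After introducing time-to-event models for the primary and secondary outcomes of Aim 2, the plan says: "We will report adjusted hazard ratios of SLNB on these outcomes".
- **Check.** "The proportional hazards assumption will be evaluated for each model using a variety of methods". The methods listed are survival plots, log(-log) plots, and "Schoenfield residuals, and covariate x time interactions". No test level is given, nor any rule for combining the methods.
- **Consequence.** "If the proportional hazards assumption is violated, we will instead use parametric survival models". One of six families is then selected by information criteria (AIC and BIC): lognormal, loglog, Gompertz, Weibull, exponential or generalized gamma.
- **Terms in the models.** "All time-to-event models will incorporate a shared frailty term for the matching group, and will include covariates that are not balanced by matching". The next sentence adds: "These models will allow us to test for association between various factors (grade, tumor size, and estrogen receptor status) and outcomes".

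The section Expected outcomes of the study mentions odds, rate and hazard ratios only as examples of what will be estimated. It names no measure for SLNB in case the Cox model is dropped.

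**The concern.** The check applies to a whole model, and the remedy replaces a whole model. Proportionality, however, is a property of each term. Every Aim 2 model contains SLNB, any covariates left unbalanced by matching, and the three tumour factors whose associations are to be tested. Nothing confines the trigger to SLNB, and there is no milder step for a covariate that fails alone.

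What is at stake is a consistent SLNB effect measure. Aim 2 has three primary outcomes (breast cancer mortality, ipsilateral invasive cancer, treated recurrence) and two secondary ones (overall survival, lasting side effects). The plan uses overall survival as a benchmark for model performance, and it stratifies by radiation therapy, DCIS characteristics and life expectancy to find patients who might forgo SLNB. Both uses are easier to interpret when the SLNB effect is on one scale. If one model yields a hazard ratio and another a time ratio because an adjustment covariate behaved differently, the contrast between them partly reflects the choice of model.

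**Working it through.** The plan gives no sample size, event count or test level for this analysis, so there is no figure of its own to reproduce. The check has three parts.

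**1. What each fallback does when a covariate other than SLNB is non-proportional**

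| Family listed in the plan | Repairs the covariate's violation? | Constant SLNB hazard ratio? |
|---|---|---|
| Exponential, Weibull, Gompertz | No; as usually fitted, these are proportional hazards models | Yes |
| Lognormal, loglog (read as log-logistic), generalized gamma | Not specifically; they change the model for every term | Not in general |

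Neither row targets the covariate that failed. A time interaction for that covariate, or stratification on it, does.

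**2. Chance trigger when every term is proportional (illustration)**

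Assumptions, none from the plan: k independent tests, each at 5%, with one flag enough to switch.

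P(at least one flag) = 1 − 0.95^k

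- k = 1 (SLNB only): 1 − 0.95 = 5%.
- k = 4 (SLNB, grade, size, receptor status): 1 − 0.8145 = 18.5%, about 19%.
- k = 10 (many unbalanced covariates): 1 − 0.5987 = 40.1%.

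A single global test would trigger at about 5% whatever the value of k.

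**3. Simulation of the mechanism (settings assumed)**

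*Strong violation.* There were 150 datasets of 3,000 patients, one third with SLNB (as in 2:1 matching), and about 393 events each. The SLNB hazard ratio was constant at 0.80. One covariate had hazard ratio 4 to year 4 and 0.8 afterwards. Schoenfeld-residual tests were run at 5%, and AIC chose among five families (generalized gamma and frailty omitted).

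- SLNB was flagged in 5 of 150 datasets (3.3%) and the covariate in 149 of 150 (99.3%). Cox was dropped in 99.3% under an any-term trigger.
- Of the 149 switches, AIC chose lognormal in 145 and Gompertz in 4.
- The Cox model being discarded estimated the SLNB hazard ratio at 0.79 (true 0.80).

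*No violation, same design.* The switch occurred in 10 of 150 datasets (6.7%). AIC then chose exponential 6 times, Weibull once, Gompertz once and log-logistic twice, so 8 of 10 switches kept a hazard ratio.

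*Second setting.* There were 200 cohorts of 6,000 with about 473 events each, SLNB hazard ratio 0.70, and grade hazard ratio 4 for 3 years and then 1. The SLNB estimates were 0.695 (Cox), 0.696 (Cox stratified by grade, same standard error of 0.105) and 0.695 (Weibull). Lognormal had a better AIC than Weibull in every run and gave a time ratio of 1.64.

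*All six families, 30 runs of 6,000, SLNB hazard ratio 0.70, no frailty.* With grade at 4 then 1, AIC chose generalized gamma in 21 of 30. With a milder violation (2 then 1.3), a family that keeps a hazard ratio was chosen in 14 of 30 runs by AIC and 20 of 30 by BIC.

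The simulations show that the switch can happen with SLNB proportional, that it need not improve the SLNB estimate, and that loss of the hazard ratio depends strongly on the assumed violation.

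**The case against.** The plan does not say that any flag on any covariate forces a switch. It describes a joint look at plots, residuals and interactions, and the sentence just before concerns SLNB hazard ratios. A reader could fairly take the check to be mainly about SLNB. That stands: the defect is an unspecified trigger, not an explicit any-flag rule. It does not remove the point, because the check is stated per model and includes "covariate x time interactions", which reaches beyond SLNB on a plain reading.

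The chance figures rest on assumed tests. Since matching already covers many factors, few covariates may remain to be adjusted for. The strong simulated violations are not taken from the documents either. Both objections stand, so the figures show a mechanism and not an expected rate.

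Grade, size and receptor status are factors of interest, so checking proportionality for them is proper, and stratifying on one would remove an estimate the plan intends to give. This stands and shapes the fix.

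An SLNB-only trigger would still leave no effect measure named if SLNB itself failed. This also stands, and the fix has to cover it.

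A reader might go further and infer that the SLNB estimate would be biased, that its hazard ratio would usually be lost, or that results could not be compared at all. The documents do not support these. Cox and Weibull agreed in the check (both 0.695), three of the six families keep a hazard ratio, and the primary outcomes are separate endpoints that can each be reported.

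**Conclusion.** The point holds in a limited form. As written, non-proportionality of a term other than SLNB can replace the Cox model for SLNB. The stated remedy does not address a covariate-specific violation: three of the six families keep the same constraint, and the other three generally do not deliver the promised constant hazard ratio. The SLNB effect measure may therefore vary across Aim 2 outcomes and strata for reasons unrelated to SLNB.

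The frequency cannot be derived from the documents. The 19% per model assumes four independent 5% tests with one flag sufficient; under a single global 5% test it would be about 5%. This is more than a missing detail, because the plan commits to a remedy that does not fit the problem, but it is inexpensive to correct.

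**What to change.** In the multivariable paragraph of Data management and statistical analysis:

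1. Base any change in how the SLNB effect is modelled on evidence of non-proportionality for the SLNB term only, and state which diagnostic decides and at what level.
2. If another covariate is non-proportional, keep the Cox model. Add a time interaction for that covariate; this is preferred for grade, tumour size and receptor status, whose associations are to be reported. Stratify on the covariate if it serves only for adjustment.
3. Name one SLNB effect measure to report if SLNB itself is non-proportional, for instance hazard ratios over periods fixed in advance or a restricted mean time difference to a stated horizon.
4. Apply the same rule to every Aim 2 outcome and stratum.

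The cost is a few sentences and no new data. There is a small downside: a covariate used as a stratum has no hazard ratio, and one with a time interaction has no single hazard ratio. If the authors already meant the check for SLNB alone, items 1 and 2 only make that explicit.
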